10.8 Resistance Analyses

10.8.1 HCV Drug-Resistance Analyses

Full length NS3/4A or NS5A from all available baseline samples will be sequenced by next generation sequencing (NGS). For subjects who experience virologic failure (on-treatment virologic failure or post-treatment relapse as defined in Section 10.1), full length NS3/4A and NS5A genes from the first available sample after virologic failure with HCV RNA ≥ 1000 IU/mL will be sequenced by NGS. An appropriate subtype specific prototypic reference sequence will be used for comparison with sequences from samples. Subjects who experience virologic failure will be referred to as subjects in the primary virologic failure (PVF) population, and a listing by subject that includes HCV genotype/subtype, IL28B genotype, reason for SVR₁₂ non-response, time point(s) sequenced as closest to time of VF, and HCV RNA value at the VF time point(s) will be produced for these subjects. In addition, all listings described below will display HCV genotype/subtype and reason for SVR₁₂ non-response in the subject identifier for each subject. A separate listing will summarize all subjects in the PVF population for whom no sequencing was performed (e.g., lost to follow-up while HCV RNA ≤ 1000 IU/mL).

Subjects treated with study drug who do not achieve SVR₁₂ due to reasons other than virologic failure (prematurely discontinued study drug with no on-treatment virologic failure, HCV reinfection, missing SVR₁₂ data or other reasons as described in Section 10.1, Reasons for SVR₁₂ Non-Response), but have a time point with HCV RNA ≥ 1000 IU/mL after treatment discontinuation, will have the sample at that time point sequenced. These subjects will be referred to as the non-PVF population. A listing of all subjects in the non-PVF population with post-baseline sequencing available will be created that is similar to the listing of subjects in the PVF population with post-baseline sequencing available.

For each DAA target, signature amino acid positions and a key subset of amino acid positions are listed in Table 14. Appropriate subtype-specific prototypic reference sequence will be used for comparison with sequences from samples.

Table 14. List of Genotype-Specific Signature Amino Acid Positions and Key Subsets of Amino Acid Positions

Genotype	Signature Amino Acid Positions	Key Subset of Amino Acid Positions
NS3/4A		
1a	36, 43, 54, 55, 56, 80, 107, 122, 132, 155, 156, 158, 168, and 170	155, 156, 168
1b	36, 54, 55, 56, 80, 107, 122, 155, 156, 158, 168, 170, and 175	155, 156, 168
2, 3, 4, 5, 6, 1 – other (non 1a/1b)	36, 43, 54, 55, 56, 80, 155, 156, 166 (GT3 only) and 168	155, 156, 168
NS5A		
1a	24, 28, 29, 30, 31, 32, 58, 62, 92, and 93	24, 28, 30, 31, 58, 92, 93
1b	24, 28, 29, 30, 31, 32, 54, 58, 62, 92, and 93	24, 28, 30, 31, 58, 92, 93
2, 3, 4, 5, 6, 1 – other (non 1a/1b)	24, 28, 29, 30, 31, 32, 58, 92, and 93	24, 28, 30, 31, 58, 92, 93

Included time points for analyses on samples from subjects who do not achieve SVR₁₂ are 1) the sample closest in time after failure/discontinuation with an HCV RNA level of ≥ 1000 IU/mL, and 2) 24 weeks post-DAA treatment, provided that resistance-associated variants were detected at the time of failure/discontinuation.

The following definitions will be used in the resistance analyses:

- Baseline polymorphism: a polymorphism by NGS in a baseline sample ($\geq 2\%$ or $\geq 15\%$ prevalence within a subject's viral population depending on frequency threshold utilized) that was not present in the appropriate prototypic reference amino acid sequence for a given DAA target (NS3/4A or NS5A)
- Variant at signature amino acid position: variant (relative to reference) present by NGS at a detection threshold of 2% or 15% (depending on frequency threshold utilized) in a baseline or a post-baseline sample at a signature amino acid position
- Post-baseline variant: an amino acid variant in a post-baseline time point sample that was not detected at baseline ($< 2\%$) in the subject and is detectable in $\geq 2\%$ of the sequences from the post-baseline sample

- Enriched variant: variant present in both the baseline and a post-baseline sample whose prevalence in the post-baseline sample is at least 20 percentage points greater than the prevalence in the baseline sample [(post-baseline % – baseline %) ≥ 20]
- Treatment-emergent variant by NGS: A post-baseline variant or an enriched variant

Analysis will be performed separately for each cohort by HCV genotype/subtype within each listing.

Analysis 1: The following analyses will be performed for all subjects:

- A listing of all baseline polymorphisms (2% detection threshold) at signature amino acid positions for each DAA target (NS3 and NS5A) (ITT).
- The number and percentage of subjects with baseline polymorphisms at detection-thresholds of 2% and 15% at signature amino acid positions (ITT). This table includes prevalence of each baseline polymorphism, and a summary of the number of subjects with polymorphisms in NS3 only, NS5A only, any in NS3, any in NS5A, any in NS3 or NS5A, and any in NS3 + NS5A.
- Total number and percentage of subjects with baseline polymorphisms *at the key subset of amino acid positions* in NS3 only, NS5A only, any in NS3, any in NS5A, any in NS3 or NS5A, and any in NS3 + NS5A (ITT), by subtype, and total.
- Total number and percentage of subjects with baseline polymorphisms *at the key subset of amino acid positions* in NS3 only, NS5A only, any in NS3, any in NS5A, any in NS3 or NS5A, and any in NS3 + NS5A (ITT), by genotype, and total.

Analysis 2: Analysis 2 will be applicable to Cohort 1 only. The impact of baseline polymorphisms on treatment outcome will be assessed for the **mITT-VF** population as follows: for each polymorphism, the SVR₁₂ rate will be calculated for subjects with and without the polymorphism and the two rates will be compared using Fisher's exact test. Analysis will be grouped by HCV genotype/subtype and DAA target (NS3 or NS5A).

The analysis will include the number of subjects within each genotype/subtype with variants in NS3 only, NS5A only, any in NS3, any in NS5A, any in NS3 or NS5A, and any in NS3 + NS5A.

The following will be included in the analyses of impact of baseline polymorphisms on treatment outcome:

- Polymorphisms at signature amino acid positions (vs no polymorphism at that position), using detection thresholds of both 2% and 15%. The analysis will include the number of subjects with polymorphisms in NS3 only, in NS5A only, any in NS3, any in NS5A, any in NS3 or NS5A, and any in NS3 + NS5A.
- Each polymorphism at signature amino acid position (vs not that polymorphism) using detection thresholds of 2% and 15%. The analysis will include the number of subjects with polymorphisms in NS3 only, in NS5A only, any in NS3, any in NS5A, any in NS3 or NS5A, and any in NS3 + NS5A.

Analysis 3: Analysis 3 will be applicable to Cohort 1 only. In subjects with or without baseline polymorphisms in NS3 only, in NS5A only, any in NS3, any in NS5A, any in NS3 or NS5A, and any in NS3 + NS5A at the *key subset of amino acid positions* at 15% detection threshold, the SVR₁₂ rate will be calculated, and the rates with or without polymorphisms will be compared using Fisher's exact test. Analysis will be separated by HCV subtype. The following tables will be provided (mITT-VF):

- Comparison of SVR₁₂ rates by subtype, and total (including all subtypes)
- Comparison of SVR₁₂ rates by genotype, and total (including all genotypes)

Analysis 4:

The following analyses will be performed for subjects who do not achieve SVR₁₂ (with separate summaries for subjects in PVF and non-PVF populations) and have post-baseline resistance data available:

- Listings by subject of all *treatment-emergent variants* relative to the baseline amino acid sequences will be provided for each DAA target (NS3/4A and NS5A).
- Listings by subject of all *variants at signature amino acid positions* in a post-baseline time point for each DAA target (NS3 and NS5A).
- The persistence of post-baseline variants at signature resistance-associated amino acid positions for each target (NS3 and NS5A) from subjects will be assessed at Post-Treatment Week 24. Listings by subject and time point of all treatment-emergent variants will be provided for each DAA target (NS3 and NS5A).

HCV Genotype/Subtype

Phylogenetic analysis will be conducted on HCV sequence from baseline samples for all subjects in Part 1, and from subjects with available sample in Part 2 in order to accurately determine subtype.

Subjects' HCV genotype and subtype may be assessed based on the Inno-LiPA 2.0 Assay used by the Central lab (Covance), the HCV genotype determination by Sanger sequencing a region of NS5B by the Central lab (Covance) and/or from phylogenetic analysis of the full length NS3/4A, and/or NS5A sequences performed by AbbVie. If the phylogenetic analysis is available, then it will be used to determine the subject's HCV genotype and subtype. If it is not available, then the Sanger sequencing assay result will be used to determine the subject's HCV genotype and subtype, if available. Finally, if neither the phylogenetic analysis result nor the Sanger sequencing assay results is available, then the Inno-LiPA assay results will be used to categorize the subject. This subtype information will be used in summaries of efficacy subgroup analyses. The baseline characteristic summary will use the results from the central laboratory (Sanger sequencing or Inno-LiPA 2.0 Assay [if Sanger sequencing not available]).

A summary of HCV subtype as provided by the central laboratory (Sanger sequencing or Inno-LiPA 2.0 Assay [if Sanger sequencing not available]) versus phylogenetic analysis also will be provided.

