**Resistance:**

The polymorphisms at signature resistance-associated amino acid positions at baseline will be tabulated and summarized for all subjects receiving study drugs in Part 1. For subjects in Part 2 of the study, baseline polymorphisms will be determined based on availability of samples. For all subjects who experience virologic failure and have an HCV RNA  $\geq 1000$  IU/mL, post-baseline substitutions relative to the baseline sequence and to the appropriate prototypic reference sequence will be tabulated and summarized.

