### **Impact of Baseline Polymorphisms on Treatment Outcome**

The association between baseline polymorphisms and treatment outcome in subjects who receive GLE 300 mg QD with PIB 120 mg QD in the registrational or supportive Phase 2 studies was evaluated by conducting an integrated analysis of baseline sequence data. Next-generation sequencing (NGS) was conducted on all baseline samples at 15% detection threshold at key amino acid positions 155, 156, and 168 in NS3, and 24, 28, 30, 31, 58, 92, and 93 in NS5A.

In subjects who were TN or TE-PRS, baseline polymorphisms in NS3 were detected in 1.1% (9/845), 0.8% (3/398), 1.6% (10/613), 1.2% (2/164), 41.9% (13/31), and 2.9% (1/34) of subjects with HCV genotype 1, 2, 3, 4, 5 and 6-infection, respectively. Baseline polymorphisms in NS5A were detected in 26.8% (225/841), 79.8% (331/415), 22.1% (136/615), 49.7% (80/161), 12.9% (4/31), and 54.1% (20/37) of subjects with HCV genotype 1, 2, 3, 4, 5, and 6-infection, respectively.

The presence of baseline polymorphisms in NS3 and/or NS5A did not have an impact on SVR12 rates for GT1, 2, 4, 5, or 6-infected subjects.

Within GT3-infected subjects, baseline polymorphisms in NS3 and the NS5A polymorphisms at positions 24, 28, 31, 58, 92, or 93 did not have an impact on treatment outcome.

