### **HCV Resistance Testing Plasma Sample**

A plasma sample for baseline HCV resistance testing will be collected on Day 1 from all subjects in Part 1, and from subjects in Part 2 in which the sample for baseline HCV resistance testing will be within the allowable blood volume limits. HCV resistance testing is required for all subjects who meet virologic failure criteria at the visits indicated in [Appendix C](#). Specific instructions for preparation and storage of the samples will be provided by the central laboratory, the Sponsor, or its designee.

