**Table 12. Signature Amino Acid Positions and the Key Subset of Amino Acid Positions**

Target	Signature Amino Acid Positions	Key Subset of Amino Acid Positions
GT1 NS3	36, 43 (GT1a only), 54, 55, 56, 80, 107, 122, 132 (GT1a only), 155, 156, 158, 168, 170, 175 (GT1b only)	155, 156, 168 (all GTs)
GT2, 4, 5, 6 NS3	36, 43, 54, 55, 56, 80, 155, 156, 168	
GT1 NS5A	24, 28, 29, 30, 31, 32, 54 (GT1b only), 58, 62, 92, 93	24, 28, 30, 31, 58, 92, 93 (all GTs)
GT2, 4, 5, 6 NS5A	24, 28, 29, 30, 31, 32, 58, 92, 93	

The following definitions will be used in the resistance analyses:

- Baseline polymorphism: an amino acid polymorphism by NGS in a baseline sample ( $\geq 2\%$  or  $\geq 15\%$  prevalence within a subject's viral population depending on polymorphism frequency threshold utilized) that was not present in the appropriate prototypic reference amino acid sequence for a given DAA target (NS3/4A or NS5A).
- Polymorphism/substitution at signature amino acid position: polymorphism (relative to reference) present in a baseline or substitution (relative to baseline) present in a post-baseline sample at a signature amino acid position.
- Post-baseline substitution: an amino acid substitution in a post-baseline time point sample that was not detected at baseline ( $< 2\%$ ) in the subject and is detectable in  $\geq 2\%$  of the sequences from the post-baseline sample.

- Enriched polymorphism: polymorphism present in both the baseline and a post-baseline sample whose prevalence in the post-baseline sample is at least 20 percentage points greater than the prevalence in the baseline sample [(post-baseline % – baseline %) ≥ 20].
- Treatment-emergent substitution by NGS: A post-baseline substitution or an enriched polymorphism.

**Analysis 1:** The following analyses will be provided for all subjects with baseline sequence data, separated by HCV subtype:

- A listing of all baseline polymorphisms (2% detection threshold) at signature resistance-associated amino acid positions for each DAA target (NS3/4A and NS5A).
- A listing of all baseline polymorphisms (15% detection threshold) at non-signature resistance-associated amino acid positions for each DAA target (NS3/4A and NS5A) for subjects who experience virologic failure.

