5.1.1 Intention-to-Treat (ITT) Population

All subjects who receive at least one dose of study drug will be included in the ITT population. Demographic, baseline characteristic, exposure, concomitant medication and medical history analyses will be performed on the ITT population overall and by age group. Efficacy analyses will be performed on the ITT population.

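### SAP Analysis 1 sets baseline polymorphism prevalence on the ITT population, so Part 2 children without a baseline sequence would dilute the percentages; the denominator should be the sequenced subjects, as in the protocol

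*SAP*

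**What the plan says.** In SAP 10.8.1 the opening line of Analysis 1 is "The following analyses will be performed for all subjects". Three number-and-percentage tables follow: signature positions, key positions by subtype, and key positions by genotype. The first is specified as "The number and percentage of subjects with baseline polymorphisms at detection-thresholds of 2% and 15% at signature amino acid positions (ITT", ending in the population label, and the other two carry the same label. SAP 5.1.1 defines it: "All subjects who receive at least one dose of study drug will be included in the ITT population".

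The protocol's version of Analysis 1 (8.1.6.1, after Table 12) has a narrower base: "The following analyses will be provided for all subjects with baseline sequence data, separated by HCV subtype".

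Not every child will have a sequence. Protocol 5.3.1.1 (HCV Resistance Testing Plasma Sample) takes the Day 1 sample from everyone in Part 1, but "from subjects in Part 2 in which the sample for baseline HCV resistance testing will be within the allowable blood volume limits". The resistance paragraph of the synopsis agrees: "For subjects in Part 2 of the study, baseline polymorphisms will be determined based on availability of samples". SAP 10.8.1 itself sequences only the baseline samples that are available.

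**The concern.** A child with no sequence has an unknown status, not a wild-type one. If that child stays in the denominator and cannot enter the numerator, the table treats unknown as negative. SAP 10.8.1 asks for output by cohort. Part 1 is meant to be fully sampled and Part 2 is not, so the two Parts could appear to differ in baseline polymorphisms only because of who was sampled.

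The paediatric percentages would also not be on the same footing as the adult ones in Protocol 3.0, which use sequenced subjects as denominator. Viral variants in subjects with available samples belong to a stated secondary objective (Protocol 4.2, SAP 4.1), so the tables will be read.

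**Working it through.** **1. Reproduce the documents' own prevalence figures.** Protocol 3.0 (Impact of Baseline Polymorphisms on Treatment Outcome) states, for genotype 1, "Baseline polymorphisms in NS5A were detected in 26.8% (225/841" as numerator and denominator. The ITT totals come from Protocol Table 3, treatment-naïve plus TE-PRS subjects. Prevalence is x/n.

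| NS5A | x / sequenced | stated | x / ITT N | sequenced fraction |
|---|---|---|---|---|
| GT1 | 225/841 = 26.8% | 26.8% | 225/889 = 25.3% | 0.946 |
| GT2 | 331/415 = 79.8% | 79.8% | 331/466 = 71.0% | 0.891 |
| GT3 | 136/615 = 22.1% | 22.1% | 136/643 = 21.2% | 0.956 |
| GT4 | 80/161 = 49.7% | 49.7% | 80/178 = 44.9% | 0.904 |
| GT5 | 4/31 = 12.9% | 12.9% | 4/32 = 12.5% | 0.969 |
| GT6 | 20/37 = 54.1% | 54.1% | 20/48 = 41.7% | 0.771 |

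All six stated values reproduce on the sequenced denominator. On the ITT denominator every one falls, most in GT6, where the sequenced fraction is lowest.

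**2. The general formula.** Let p be prevalence among sequenced subjects and s the sequenced fraction. The percentage on ITT is x/N = (x/n) × (n/N) = p × s. On the sequenced denominator it is p, whatever s is.

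**3. Size in this trial.** Protocol 5.1 plans about 44 subjects in Part 1 and 81 in Part 2, 125 in all. The share u of Part 2 without a sequence is not given and is an assumption here; Part 1 is taken as fully sequenced. The pooled factor is (44 + 81(1 − u))/125:

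- u = 0.25: 104.75/125 = 0.84
- u = 0.50: 84.5/125 = 0.68
- u = 0.75: 64.25/125 = 0.51

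Within a Part 2 cohort the factor is that cohort's own 1 − u, and in Part 1 it is 1. With the SAP's total of 110 (44 + 66) the pooled factors are 93.5/110 = 0.85, 77/110 = 0.70 and 60.5/110 = 0.55.

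**4. Subjects with one target sequenced.** In the adult data the NS3 and NS5A denominators differ (GT1: 845 and 841; GT2: 398 and 415), so this can happen. Suppose a missing target is treated as negative:

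- NS3 positive, NS5A missing: the subject enters the NS3-only row, although NS5A might be positive too. That row can be too high and the NS3 + NS5A row too low. The mirror case affects the NS5A-only row.
- NS3 negative, NS5A missing: the subject counts as having nothing, which can lower the NS5A-only row and the row for either target.

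The net direction in the two single-target rows is therefore not fixed.

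**The case against.** The best reply is that the ITT label names a population and is not a denominator formula. No sentence in the SAP says that unsequenced children count as negative. A baseline polymorphism is defined there as something found by sequencing a baseline sample, and the SAP objective refers to subjects with available samples. The label may serve only to separate Analysis 1 from Analyses 2 and 3, which use mITT-VF. A programmer who also had the protocol would probably use sequenced subjects.

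That is plausible, but Analysis 1 does not say it. Elsewhere the SAP writes such restrictions out: Analysis 4 requires available post-baseline resistance data, the relapse analysis requires a post-treatment value (10.1), and baseline APRI and FIB-4 exclude subjects with missing components (7.1). The literal reading of Analysis 1 gives the wrong percentage.

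Other parts of the reply stand, and they rule out stronger readings that a reader might infer:

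- **A deliberate change of base.** SAP 1.0 was written against Amendment 1 of July 2017, while the protocol text compared here is dated March 2019. SAP 12.1 lists no change to this base. The documents show a disagreement, not an intention.
- **A false trend by age, worst in the youngest.** Blood-volume limits make this a reasonable guess, but no sampling rate by age or weight is given. Footnote t of Protocol Appendix C even describes the Day 1 sample without a condition, so the missing share could be small.
- **Understatement in every row.** Step 4 of the working shows that the single-target rows can be inflated.
- **Scaling the adult 26.8% to the paediatric total.** That figure is for adult genotype 1, NS5A, key positions, 15% threshold. The main paediatric table covers signature positions at two thresholds, and the children span genotypes 1 to 6.

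**Conclusion.** The point holds as a mismatch between SAP and protocol in which the SAP's literal wording gives a biased percentage. On that wording, prevalence is multiplied by the sequenced fraction: pooled, 0.84, 0.68 or 0.51 if 25%, 50% or 75% of Part 2 is unsequenced, and the full sequenced fraction within a Part 2 cohort. The bias goes to zero if nearly every child is sampled. These figures rest on an assumed missing share and on complete sequencing in Part 1.

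A spurious contrast between Parts 1 and 2 is a real possibility; a gradient within Part 2 is only an inference.

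The reach is limited. A reader might fear for the efficacy conclusions, but the analyses that relate polymorphisms to SVR12 (Analyses 2 and 3) are confined to Cohort 1, where a baseline sample is planned for all. PK and SVR12 do not depend on Analysis 1. The tables are descriptive, and the correction is worth making because it is specific and nearly free.

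**What to change.** In SAP 10.8.1, Analysis 1, replace the ITT label on the three percentage tables with an explicit denominator, in line with Protocol 8.1.6.1:

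- rows for a single target (any in NS3, any in NS5A, and individual positions or polymorphisms): subjects with a baseline sequence for that target;
- rows that combine targets (NS3 only, NS5A only, either, both): subjects with both targets sequenced at baseline.

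Beside each table, print the number sequenced out of the ITT number by cohort and genotype/subtype, so that the reader can see how much of each Part 2 cohort the percentage describes.

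The cost is a wording change, three table denominators and one added count. No new data are needed.
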